#### Preliminary clinical efficacy data for multi-kinase inhibitors in ACC

Evidence for both MYB-dependent and -independent mechanisms of VEGFR/c-kit/FGFR activation in ACC biology has raised interest in evaluating multikinase inhibitors against

IRB#: 13-244 A(9)

these targets in ACC patients. Preliminarily, studies have suggested clinical activity with these agents. The first study conducted was a phase II trial of sunitinib (VEGFR, PDGFR, KIT inhibitor) in patients with progressive, recurrent/metastatic ACC. While no responses were observed, 8 out of the enrolled 14 patients had stable disease for 6 months or more, potentially meaningful given that progressive disease was required for enrollment. Results from a sorafenib (VEGFR, PDGFR inhibitor) and a dovitinib (VEGFR, PDGFR, FGFR1-3, KIT inhibitor) phase II ACC trial were reported in abstract form at the 2013 ASCO Annual meeting. Both agents elicited an approximately 11% response rate. An axitinib (VEGFR, PDGFR, c-kit inhibitor) phase II study also recently completed enrollment at MSKCC. The data has not yet been presented, but the study was a 2-stage design that met the clinical efficacy rule required for progressing to the second stage. These preliminary data suggest that combined VEGFR, PDGFR, c-kit inhibition plus or minus FGFR targeting translates to some clinical efficacy in ACC.

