#### 9.4 Correlative Studies

Exploratory Objective: To perform tumor tissues analyses for biomarkers that correlate to regorafenib clinical efficacy.

- 9.4.1 Background Studies/Preliminary Data: We hypothesize that ACC responses to regorafenib will be linked to baseline activation of the vascular endothelial growth factor (VEGF), platelet-derived growth factor (PDGF), fibroblast growth factor receptor (FGF), and/or c-kit (CD117) pathways via overexpression of the oncogenic transcription factor c-myb and/or other mechanisms outlined in Section 3.0. In order to evaluate this hypothesis, the studies described below will be performed upon both archival and research biopsy tissues, depending on the availability of funding. Included amongst these studies are exploratory approaches that may also suggest myb-independent mechanisms that may mediate drug susceptibility or resistance.
- 9.4.2 Study Plan for fixed tissue: Studies evaluating c-myb protein expression, t(6;9) translocation status, the VEGF/PDGF/FGF/KIT pathways, and other potentially relevant genes/proteins will be conducted in fixed tissues.

Expression of VEGF/PDGF/FGF/KIT pathway proteins will be evaluated by immunohistochemistry (IHC). c-myb expression will also be evaluated by IHC. The presence or absence of the t(6;9) translocation will be assessed by fluorescent insitu hybridization (FISH). These studies will be performed upon collected archival

IRB#: 13-244 A(9)

samples and/or the fixed portions of the research biopsies obtained on this study, depending on the availability of tissue. Evaluation of the t(6;9) fusion breakpoint may also be pursued with RT-PCR cDNA amplification and sequencing if feasible, though the need for high yield and quality RNA to perform this analysis may necessitate using frozen tissues obtained from the research biopsies.

We anticipate that all 38 patients will have archival tissue available for these analyses. We will explore correlations between the tumor IHC status of the target proteins listed above, as well as presence of the t(6;9) translocation, with clinical benefit from regorafenib. Please see Section14.0 for biostatistical considerations for these studies.

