Target lesions. All measurable lesions up to a maximum of 2 lesions per organ and 5 lesions in total, representative of all involved organs, should be identified as **target lesions** and recorded and measured at baseline. Target lesions should be selected on the basis of their size (lesions with the longest diameter), be representative of all involved organs, but in addition should be those that lend themselves to reproducible repeated measurements. It may be the case that, on occasion, the largest lesion does not lend itself to reproducible measurement in which circumstance the next largest lesion which can be measured reproducibly should be selected. A sum of the diameters (longest for non-nodal lesions, short axis for nodal lesions) for all target lesions will be calculated and reported as the baseline sum diameters. If lymph nodes are to be included in the sum, then only the short axis is added into the sum. The baseline sum diameters will be used as reference to further characterize any objective tumor regression in the measurable dimension of the disease.

Non-target lesions. All other lesions (or sites of disease) including any measurable lesions over and above the 5 target lesions should be identified as **non-target lesions** and should also be recorded at baseline. Measurements of these lesions are not required, but the presence, absence, or in rare cases unequivocal progression of each should be noted throughout follow-up.

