#### 12.4 Response Criteria

#### 12.4.1 Evaluation of Target Lesions

Complete Response (CR): Disappearance of all target lesions. Any

pathological lymph nodes (whether target or nontarget) must have reduction in short axis to <10

mm.

Partial Response (PR): At least a 30% decrease in the sum of the

diameters of target lesions, taking as reference

the baseline sum diameters.

Progressive Disease (PD): At least a 20% increase in the sum of the

diameters of target lesions, taking as reference the smallest sum on study (this includes the baseline sum if that is the smallest on study). In addition to the relative increase of 20%, the sum must also demonstrate an absolute increase of at least 5 mm. (Note: the appearance of one or

more new lesions is also considered

progressions).

Stable Disease (SD): Neither sufficient shrinkage to qualify for PR nor

sufficient increase to qualify for PD, taking as reference the smallest sum diameters while on

study.

(RB PB

IRB#: 13-244 A(9)

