studied population is > 40% with a one-sided type I error of 5% and power of 90%, at least 21 of the 38 patients enrolled need to be alive and free of progression at the 6-month time point (exact binomial design).

Assuming that 6-month PFS and BOR are independent, the overall type 1 error is <0.1. The type 1 error decreases very slightly if PFS and BOR are positively correlated.

Patients who receive at least one dose of medication will be included in the evaluation of the primary objectives. Patients who do not have a recorded CR or PR and are removed from the study without a final radiologic evaluation will be classified as non-responders for BOR evaluation. If patients discontinue the study before the 6-mo PFS evaluation without evidence of progression, every effort will be made to bring them in for a 6-mo radiologic evaluation. If this is not possible, the patients will be classified as progressors for the purpose of the 6-month PFS evaluation.

The secondary endpoint is the evaluation of safety/tolerability of regorafenib.

Safety will be assessed in terms of AEs, laboratory data and vital sign data, which will be collected for all patients. Appropriate summaries of these data will be presented. AE will be listed individually per patient according to CTCAE version 4.0, and the number of patients experiencing each AE will be summarized. The safety population will comprise all patients who receive at least one dose of study treatment.

Due to the limited sample size, the analyses investigating the association between correlative markers and response to therapy will be exploratory. Levels of c-kit, VEGF, VEGFR, PDGF, PDGFR, in archival tumor tissue will be quantified by immunohistochemistry (IHC) and their association with objective response to regorafenib will be investigated using the non-parametric Wilcoxon rank-sum test. Similarly, association between c-myb (strong staining, 2+ vs other) or t(6;9) translocation and response will be tested using Fisher's exact test.

We will investigate, in an exploratory fashion, whether gene alterations that we detect are associated with response. Further, we will use linear models for microarray data (LIMMA), which performs moderated t-tests by discounting changes in low expressing genes with low variance, to identify genes who are differentially expressed between responders and non-responders. Multiplicity correction will be undertaken by controlling the false discovery rate.

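### Section 14.0 relates every tumor marker only to responder status; prespecifying best percent change in the target-lesion sum beside it would recover power at no cost in data

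*Combined protocol and SAP*

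**What the plan says.** Protocol Section 14.0 describes four groups of marker analyses, and all use response as the outcome.

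- IHC levels of c-kit, VEGF, VEGFR, PDGF and PDGFR: "their association with objective response to regorafenib will be investigated using the non-parametric Wilcoxon rank-sum test".
- c-myb staining and the translocation: "association between c-myb (strong staining, 2+ vs other) or t(6;9) translocation and response will be tested using Fisher's exact test".
- Gene alterations: the plan will explore "whether gene alterations that we detect are associated with response" and names no test.
- Expression arrays: LIMMA is used "to identify genes who are differentially expressed between responders and non-responders", with false discovery rate control.

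Response is CR plus PR by RECIST v1.1. On target lesions, PR begins at this boundary (Section 12.4.1): "At least a 30% decrease in the sum of the" target-lesion diameters relative to baseline. Measurable disease is an entry criterion (Section 6.1). Section 12.2 has the sum calculated at baseline and adds: "The baseline sum diameters will be used as reference to further characterize any objective tumor regression in the measurable dimension of the disease". Scans follow about every 8 weeks (Section 10.0). Best percent change is not named as an endpoint anywhere.

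Section 9.4.2 words the aim differently. It will correlate IHC status, "as well as presence of the t(6;9) translocation, with clinical benefit from regorafenib", but it does not define that benefit and sends the reader to Section 14.0. Section 14.0 calls the marker analyses exploratory because of the limited sample size.

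**The concern.** Few responders are expected: about 8 of 38 at the planned 20% rate, 5 at the success threshold and 2 at the null rate. Splitting patients there puts a tumor that shrank by 28% in the same group as one that grew by 40%. If a marker tracks the degree of shrinkage, most of that signal lies among the non-responders and is not used.

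A trial with no responses is a real possibility in this disease. Of the sunitinib trial Section 3.0 reports: "While no responses were observed, 8 out of the enrolled 14 patients had stable disease for 6 months or more". This trial can also succeed on 6-month PFS alone, so it could be positive with very few responders. The marker analyses would then have little or nothing to compare, although patients were asked to undergo research biopsies (34 expected, Section 9.4.3).

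**Working it through.** **Inputs from the protocol.** N = 38; response rate 5% (null) and 20% (alternative); success at 5 or more responses (Section 14.0). Related agents gave about 11% (Section 3.0). Archival tissue is expected from 38 patients and biopsies from 34 (Section 9.4). **Assumed:** marker-shrinkage correlation r, normality, and two-sided 0.05, because the plan gives no sidedness for the marker tests.

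**1. The plan's own figure.** Exact binomial, at least 5 of 38: type I error 0.0397 at 5% and power 0.901 at 20%. The design reproduces. The plan states no power for the marker analyses.

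**2. Information kept by the split.** If response were a cut of one normal outcome at upper-tail proportion p, efficiency relative to the uncut outcome is φ(z)²/[p(1−p)].

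| p | z | φ(z) | Efficiency | Equivalent patients (38 × efficiency) |
|---|---|---|---|---|
| 0.20 | 0.842 | 0.280 | 0.0784/0.1600 = 0.49 | 18.6 |
| 5/38 | 1.119 | 0.213 | 0.0455/0.1143 = 0.40 | 15.1 |
| 0.11 | 1.227 | 0.188 | 0.0353/0.0979 = 0.36 | 13.7 |
| 0.05 | 1.645 | 0.103 | 0.0106/0.0475 = 0.22 | 8.5 |

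**3. Simulated power, continuous marker.** Bivariate normal, n = 38, complete data.

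| r | Spearman on percent change | Wilcoxon, 8 responders | 5 | 2 |
|---|---|---|---|---|
| 0.5 | about 87% | about 58% | 44-48% | about 25% |
| 0.4 | 65-68% | about 38% | about 31% | about 17% |
| 0.3 | about 42% | about 23% | about 18% | about 11% |

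With heavy-tailed errors (t, 3 df), a coefficient of 0.4 and a 20% rate, power was 88% against 54%, which is the same direction.

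**4. Binary marker.** For a marker positive in half of patients and a latent correlation of 0.4, a rank-sum test of percent change has about 48% power. Fisher's test on response has 21%, 10% and 2% at response rates of 20%, 11% and 5%.

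The documents' own prevalence figures illustrate this. Section 3.0 cites one study with the translocation in 57% of tumors, so 0.57 × 38 ≈ 22. If there are 5 responders and all carry it, Fisher's two-sided p is [C(22,5) + C(16,5)]/C(38,5) = (26,334 + 4,368)/501,942 = 0.061. A perfect association misses 0.05. At the lower prevalences also cited there (27.7% and 35.2%), 5 responders can reach 0.05.

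**5. Very few responders.** P(0 of 38) = 0.95³⁸ = 0.142 at a 5% rate, 0.89³⁸ = 0.012 at 11%, and 0.0002 at 20%. With 0 responders, no analysis in Section 14.0 can be run. With 1, the smallest exact two-sided Wilcoxon p is 2/38 = 0.053, so 0.05 cannot be reached.

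**6. Incomplete scans.** With r = 0.5 and 15% of patients given the worst rank at random, power was about 57% for percent change against 46% for responder status. A repeat run with 8 responders before missingness gave 56% against 49%. The advantage remains but is much smaller.

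**The case against.** The strongest reply is that RECIST response is not percent change cut at −30%. It also depends on non-target lesions, new lesions and confirmation (Sections 12.4.2 and 12.4.3), and patients removed without a final scan count as non-responders. The efficiencies in step 2 are therefore model figures, not properties of this endpoint. That stands. A reader might infer that the plan demonstrably throws away half or more of its outcome information; the documents support this only under the threshold model.

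A reader might also infer that each patient has a usable percent change. Patients without a post-baseline scan have none, and step 6 shows what that costs.

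It is likewise tempting to say that the analyses have no power with 0 or 1 responders, and that this happens 43% of the time. The 43% applies only at the null 5% rate; it is 7% at 11% and 0.2% at 20%. With 1 responder a one-sided Wilcoxon can reach 1/38 = 0.026, and LIMMA can still be estimated. Only 0 responders stops everything.

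Objective response is a primary endpoint, and relating markers to it is legitimate. Nothing in the documents requires percent change to displace it. Nor does the sunitinib trial show that percent change would have captured benefit there: prolonged stable disease is a matter of duration, which best percent change does not measure.

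Finally, these analyses are exploratory, depend on funding (Section 9.4.1) and drive no decision, and an unplanned supplementary analysis remains possible. That limits the weight of the point. It does not remove the gain, and naming the outcome beforehand avoids a choice made after seeing the data.

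**Conclusion.** The point holds as a cheap, worthwhile improvement to the exploratory objective. Response is the only outcome in the marker analyses of Section 14.0, while a graded outcome can be derived from measurements already required. Under the normal threshold model, responder status keeps about 49% of the information at the planned response rate and 22% at the null rate. At r = 0.5 with complete data, the difference is about 58% against 87% power at the planned rate, and it widens as responders become fewer. At r = 0.3 it is about 23% against 42%, so percent change does not give an adequately powered marker study either.

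These sizes rest on assumed correlations, two-sided testing and n = 38. The biopsy-based work expects 34 patients, and FDR-adjusted LIMMA was not simulated. The primary endpoints, their thresholds and the go/no-go rule are untouched.

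**What to change.** In Section 14.0, prespecify best percent change from baseline in the target-lesion sum as an additional exploratory marker outcome beside objective response:

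- Spearman correlation for IHC levels;
- a rank-sum test of percent change by c-myb, t(6;9) or gene-alteration status;
- percent change as a continuous covariate in LIMMA, alongside the responder comparison.

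State a rule for patients with no post-baseline scan or with progression by new lesions, for example worst rank, with a sensitivity analysis excluding them. State the sidedness of the marker tests. Define the benefit named in Section 9.4.2 so that it matches the outcomes in Section 14.0.

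The cost is wording only: no new patients, scans or samples. The downsides are that percent change ignores new and non-target lesions, and that one more outcome adds to the multiplicity of the exploratory analyses.

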#### 15.0 RESEARCH PARTICIPANT REGISTRATION AND RANDOMIZATION PROCEDURES

#### 15.1 Research Participant Registration

Confirm eligibility as defined in the section entitled Criteria for Patient/Subject Eligibility.

Obtain informed consent, by following procedures defined in section entitled Informed Consent Procedures.

IRB PB

IRB#: 13-244 A(9)

During the registration process registering individuals will be required to complete a protocol specific Eligibility Checklist.

All participants must be registered through the Protocol Participant Registration (PPR) Office at Memorial Sloan-Kettering Cancer Center. PPR is available Monday through Friday from 8:30am – 5:30pm at [contact]. Registrations must be submitted via the PPR Electronic Registration System (http://ppr/). The completed signature page of the written consent/RA or verbal script/RA, a completed Eligibility Checklist and other relevant documents must be uploaded via the PPR Electronic Registration System.

#### 15.2 Randomization

Not applicable

#### 16.0 DATA MANAGEMENT ISSUES

A Research Study Assistant (RSA) will be assigned to the study. The responsibilities of the RSA include project compliance, data collection, abstraction and entry, data reporting, regulatory monitoring, problem resolution and prioritization, and coordinating the activities of the protocol study team.

The data collected for this study will be entered into the secure Clinical Research Database (CRDB). Source documentation will be available to support the computerized patient record.

Whole exome or genome sequencing data will be deidentified; samples will be labelled with patient study IDs to preserve links to clinical data. The deidentified genomic data will be stored to a protected server that is specifically set aside for clinical trial data.

### 16.1 Quality Assurance

Weekly registration reports will be generated to monitor patient accruals and completeness of registration data. Routine data quality reports will be generated to assess missing data and inconsistencies. Accrual rates and extent and accuracy of evaluations and follow-up will be monitored periodically throughout the study period and potential problems will be brought to the attention of the study team for discussion and action.

#### 16.2 Data and Safety Monitoring

The Data and Safety Monitoring (DSM) Plans at Memorial Sloan-Kettering Cancer Center were approved by the National Cancer Institute in September 2001. The plans address the new policies set forth by the NCI in the document entitled "Policy of the National Cancer Institute for Data and Safety Monitoring of Clinical Trials" which can be found at: http://www.cancer.gov/clinicaltrials/conducting/dsm-guidelines/page1... The DSM Plans at MSKCC were established and are monitored by the Office of Clinical Research. The MSKCC Data and Safety Monitoring Plans can be found on the MSKCC Intranet at: http://smskpsps9/dept/ocr/OCR%20Website%20Documents/Clinical%20Research%20Quality%20Assurance%20(CRQA)/MSKCC%20Data%20and%20Safety%20Monitoring%20Plan.pdf

IRB#: 13-244 A(9)

There are several different mechanisms by which clinical trials are monitored for data, safety and quality. There are institutional processes in place for quality assurance (e.g., protocol monitoring, compliance and data verification audits, therapeutic response, and staff education on clinical research QA) and departmental procedures for quality control, plus there are two institutional committees that are responsible for monitoring the activities of our clinical trials programs. The committees: *Data and Safety Monitoring Committee* (*DSMC*) for Phase I and II clinical trials, and the *Data and Safety Monitoring Board* (*DSMB*) for Phase III clinical trials, report to the Center's Research Council and Institutional Review Board.

During the protocol development and review process, each protocol is assessed for the level of risk and degree of monitoring required. Every type of protocol (e.g., NIH sponsored, in house sponsored, industrial sponsored, NCI cooperative group, etc.) will be addressed and the monitoring procedures will be established at the time of protocol activation.

IRB#: 13-244 A(9)

#### 17.0 PROTECTION OF HUMAN SUBJECTS

### Inclusion of Children in Research

This protocol/project does not include children because the number of children is limited and because the majority is already accessed by a nationwide pediatric cancer research network. This statement is based on exclusion 4b of the NIH Policy and Guidelines on the Inclusion of Children as Participants in Research Involving Human Subjects.

#### Risks, Benefits, Toxicities/side effects

Potential risks to human subjects include drug related toxicity, placement of IV catheters, phlebotomy, and possible psychological discomfort from the stresses associated with obtaining imaging studies (e.g., CT scan, PET scan). All efforts will be made to avoid any complication by completely reviewing patients' symptoms, providing appropriate management, and monitoring blood tests.

If an adverse medical event occurs, the patient will first contact the primary oncologist or the Principal Investigator. At nights and on weekends, there is an oncology physician on call at all times. Patients may either call or come directly to the urgent care center at Memorial Hospital (or to their local emergency room) to be seen. Patients suffering serious adverse reactions must be carefully followed and all follow-up information also recorded.

### Alternatives/options

Participation in this trial is voluntary. Depending on the specific details of the situation, patient options without being in a study might include:

- Other palliative chemotherapy off study.
- Participation in a different clinical trial
- · Best supportive care

### Financial Costs/Burdens

The patient will be responsible for all costs related to treatment and complications of treatment. Costs to the patient (third party insurer) will include hospitalizations, routine blood tests and diagnostic studies, office visits, baseline EKG, and doctor's fees. Patients will not be charged the cost of analysis for the research correlates. The patient also will not be charged for the subsequent research analysis of these specimens. Regorafenib is provided by Bayer and therefore is not billable to research participants.

